1.2.2.3.1 Description

Eighteen men with newly diagnosed intermediate- to high-risk prostate cancer were enrolled at the Henry

Ford Health System between May 2006 and January 2010 (42, 43). All men received a single intraprostatic injection of the second-generation Ad5-yCD/mutTK_{SR39}rep-hNIS adenovirus on day 1. The adenovirus dose was escalated from 1×10^{11} vp (cohort 1) to 5×10^{12} vp (cohort 3) in three cohorts. 5-FC + vGCV prodrug therapy was administered for 2 weeks (weekdays only). Following the adenovirus injection, subjects were administered Na^{99m}TcO₄ on various days and subjected to SPECT imaging.

The primary endpoint was acute toxicity through day 90. Secondary end points included feasibility of using hNIS as a reporter gene to monitor adenoviral gene therapy vectors non-invasively *in vivo*, volume and magnitude of gene expression in the prostate, kinetics and persistence of reporter gene expression, whole body distribution of ^{99m}TcO₄ uptake, PSA response, and 2-year prostate biopsy positivity.

1.2.2.3.2 Results

hNIS reporter gene expression (i.e., ^{99m}TcO₄ uptake) was detected in 0 of 3 (0%) subjects at 1×10^{11} vp, 6 of 8 (75%) subjects at 1×10^{12} vp, and 6 of 6 (100%) subjects at 5×10^{12} vp. Gene expression was readily detected in the prostate following injection of 1×10^{12} vp and 5×10^{12} vp (Figure 2). Serial imaging on consecutive days demonstrated that gene expression in the prostate lasted ≤ 7 days (Figure 3).

Importantly, whole body planar scans demonstrated that no reporter gene expression was detected outside of the prostate in any subject (Figure 4).

[figure not shown]

Figure 2. Non-invasive imaging of gene expression in the prostate. The subject received an intraprostatic injection of 5×10^{12} vp of the Ad5-yCD/mutTK_{SR39}rep-hNIS adenovirus on day 1. 16 mCi Na^{99m}TcO₄ was administered on days 2 and 3 and SPECT was performed 4 hours later. Day 3 images are shown. Radiotracer uptake is indicated by the colors (yellow > red > green). Activity in the urinary bladder (UB) is due to excretion of the radiotracer through that organ. Activity in the penis (Pe) is due to blood flow

through that organ. Activity in the bowel (Bo) is due to trapping. L, left; R, right; P, posterior; A, anterior.

[figure not shown]

Figure 3. Persistence of gene expression in the prostate. A subject with intermediate-risk prostate cancer received an intraprostatic injection (right side only) of Ad5-*yCD/mutTK_{SR39}rep-hNIS* (1×10^{12} vp) on day 1. $\text{Na}^{99m}\text{TcO}_4$ (16 mCi) was administered on days 2, 3, 4 and 8 and SPECT imaging (whole body and pelvic planar scans, pelvic SPECT) commenced 4 h later. hNIS gene expression (i.e., $^{99m}\text{TcO}_4^-$ uptake) was detected in the right side of the prostate on all days. L, left; R, right; P, posterior; A, anterior.

[figure not shown]

Figure 4. Whole body distribution of $^{99m}\text{TcO}_4$ uptake. A subject with intermediate-risk prostate cancer received an intraprostatic injection of Ad5-*yCD/mutTK_{SR39}rep-hNIS* (1×10^{12} vp) on day 1. $\text{Na}^{99m}\text{TcO}_4$ (16 mCi) was administered on day 4 and SPECT imaging commenced 4 h later. Shown are whole body planar scans prior to (pre-injection) and three days after (post-injection) the adenovirus injection. Activity in the salivary glands (Sal), lachrymal glands (Lac), thyroid gland and stomach are due to endogenous hNIS

expression. $\text{Na}^{99\text{m}}\text{TcO}_4$ is secreted through the urinary tract, accounting for the activity in the urinary bladder. The activity observed in the penis (Pen) and testicles (Tes) is due to blood flow through those structures. The intravenous $^{99\text{m}}\text{TcO}_4$ injection site can be seen in the post-injection scan.

1.2.2.3.3 Summary of Results in Newly Diagnosed Setting In Combination With Conformal Radiotherapy and Non-Invasive Imaging

Gene expression was readily detected in the prostate at adenovirus doses $\geq 1 \times 10^{12}$ vp. Gene expression peaked on days 2 or 3 and last ≤ 7 days in most subjects as determined by SPECT. No gene expression was detected outside the prostate in any subject. At an adenovirus dose of 5×10^{12} vp, on average, 45% of the prostate volume was covered with gene expression (43).

1.3 Interleukin 12 (IL-12) Gene Therapy

To enhance our investigational approach further, we have added IL-12 to our therapeutic platform (57). IL-12 was selected for evaluation for several reasons. IL-12 plays an essential role in the interaction between innate and adaptive immunity (58-60). It is normally produced by phagocytes (monocytes/macrophages, neutrophils) and dendritic cells in response to pathogens, and directly activates cells of the innate (NK and NK-T cells) and adaptive (CD4⁺ and CD8⁺ cells) arms of immunity. IL-12 helps to prime T cells and increases their survival, promotes Th1 differentiation, enhances T cell, NK cell, and NK-T cell effector functions, and induces the secretion of IFN- γ , which mediates many of IL-12's anti-tumor effects. IFN- γ acts directly on tumor cells as well as stromal and endothelial cells within the tumor microenvironment. IFN- γ signaling results in 1) increased MHC class I processing and presentation (enhancing recognition of tumor by T cells); 2) induction of chemokines (IP-10 and MIG) that may recruit innate and adaptive immune effectors, which in turn lead to 3) alterations in extracellular matrix remodeling, including inhibition of matrix metalloproteinase expression, that reduces angiogenesis and tumor invasion; and 4) decreased expression of adhesion molecules by endothelial cells that may further limit angiogenesis. Hence, the rationale behind IL-12 immunotherapy lies in its ability to induce IFN- γ expression, promote immune cell survival and activation, enhance productive antigen presentation, and inhibit tumor angiogenesis.

IL-12 has demonstrated significant anti-tumor activity in preclinical models including prostate cancer (61). However, its activity in the clinic has been modest when administered as a recombinant protein or expressed from retrovirally-transduced fibroblasts (59). Furthermore, IL-12 has resulted in severe toxicity including two treatment-related deaths when administered systemically as a recombinant protein (62, 63). We believe that IL-12 produced by a locally administered, oncolytic adenovirus may exhibit better activity in the clinic without excessive toxicity relative to previous approaches. Administering the adenovirus intraprostatically (rather than systemically) should result in a high, local concentration of IL-12 within the prostate. This should limit systemic toxicity and promote IL-12's anti-tumor effects. IL-12 has been well-tolerated in humans when administered locally (59). Moreover, we believe our multi-modal approach may function like an autologous, whole tumor

vaccine. All modalities (*oncolytic viral therapy, cytotoxic gene therapy, IL-12 gene therapy, and radiotherapy* when combined with radiation) result in significant tumor cell destruction and the release of tumor antigens. This may facilitate antigen cross-presentation by professional APCs, which, when coupled with IL-12's ability to promote Th1 differentiation, may lead to the development of antigen-specific, cell-mediated immunity.

We have demonstrated in a preclinical model of prostate cancer that the addition of IL-12 to our therapeutic platform improves both local and metastatic tumor control that is mediated by both the innate and adaptive arms of immunity (57).

1.4 Health-Related Quality of Life (HRQOL) and Utilities

1.4.1 Expanded Prostate Index Composite (EPIC)

The Expanded Prostate Cancer Index Composite (EPIC) is a comprehensive instrument designed to evaluate patient function and bother after prostate cancer treatment. EPIC is a robust prostate cancer HRQOL instrument that measures a broad spectrum of urinary, bowel, and sexual symptoms related to radiotherapy (64). The domains (e.g., urinary, bowel, sexual) were validated separately; since each domain will be used intact there is no threat to validity (65).

1.4.2 Utility as Measured by the EQ-5D

The EQ-5D is a two-part, self-assessment questionnaire that takes approximately 5 minutes to complete (66). The first part consists of 5 items covering 5 dimensions including: mobility, self care, usual activities, pain/discomfort, and anxiety/depression. Each dimension has an index score of 1- no problems, 2- moderate problems, or 3- extreme problems. The second part is a visual analogue scale (VAS) valuing current health state, measured on a 20-cm 10-point interval scale. Worst imaginable health state is scored as 0 at the bottom of the scale, and best imaginable health state is scored as 100 at the top. Both the 5-item index score and the VAS score are transformed into a utility score between 0 "Worst health state" and 1 "Best health state". The EQ-5D will be completed by the patient.

2.0 OBJECTIVES

2.1 Primary

The primary purpose of this phase 1 study is to determine the dose-dependent toxicity and maximum tolerated dose (MTD) of oncolytic adenovirus-mediated cytotoxic and IL-12 gene therapy in men with locally recurrent prostate cancer after definitive radiotherapy.

2.2 Secondary

To assess:

2.2.1 PSA response.

2.2.2 Freedom from biochemical/clinical failure (FFF).

2.2.3 PSA doubling time (PSADT) before and after administration of the study therapy.

2.2.4 Disease-specific and overall survival.

2.2.5 Quality of life (QOL).

2.3 Exploratory

2.3.1 Possible association between the primary and secondary outcomes and immunological endpoints including serum IL-12 and IFN- γ levels, and NK cell cytolytic activity.

3.0 SUBJECT SELECTION

3.1 Number of Subjects

Fifteen to 30 men with locally recurrent prostate cancer after definitive radiotherapy.

3.2 Criteria for Subject Eligibility

To be eligible, the subject must have:

3.2.1 Biopsy-proven local recurrence of prostate cancer at least one year after the completion of definitive radiation therapy. The biopsy must be performed within 180 days of registration.

3.2.2 Evidence of biologically active disease as demonstrated by an unequivocally rising serum PSA level that is ≥ 2 ng/mL above the nadir.

3.2.3 PSA < 100 ng/mL.

3.2.4 Age ≥ 18 years

- 3.2.5** Karnofsky performance status ≥ 70 .
- 3.2.6** Negative lymph nodes as established by imaging (pelvic CT or pelvic MRI) within 90 days of registration.
 - 3.2.6.1** Subjects with lymph nodes equivocal or questionable by imaging are eligible if the nodes are ≤ 1.0 cm.
 - 3.2.6.2** Subjects with positive lymph nodes by capromab pentetide (ProstaScint) scans are eligible provided a corresponding lymph node identified by CT or MR imaging is ≤ 1.0 cm.
- 3.2.7** No evidence of metastatic disease, as evaluated by bone scan and CT scan of the abdomen and pelvis within 90 days prior to registration. Equivocal bone scan findings are allowed if plain films are negative for metastasis.
- 3.2.8** Subjects must have adequate baseline organ function, as assessed by the following laboratory values, within 30 days before initiating the study therapy:
 - 3.2.8.1** Adequate renal function with serum creatinine ≤ 1.5 mg/dL or creatinine clearance >50 mL/min/m².
 - 3.2.8.2** Platelet count $> 100,000/\mu\text{L}$.
 - 3.2.8.3** Absolute neutrophil count $> 1,000/\mu\text{L}$.
 - 3.2.8.4** Hemoglobin > 10.0 g/dL.
 - 3.2.8.5** Bilirubin < 1.5 mg/dL
 - 3.2.8.6** AST/SGOT and ALT/SGPT < 3.0 times upper limit of normal (ULN).
- 3.2.9** Men of child-producing potential must be willing to consent to use effective contraception for at least 3 months after the gene therapy.
- 3.2.10** Subjects must possess the ability to give informed consent and express a willingness to meet all of the expected requirements of the protocol for the duration of the study.

3.3 Criteria for Subject Exclusion

Subjects with the following conditions will be excluded from the study:

- 3.3.1** PSA ≥ 100 ng/mL.
- 3.3.2** Prostate volume > 100 cc.

- 3.3.3** Pathologically positive lymph nodes or nodes > 1.0 cm on imaging. Note: nodes > 1.0 cm but biopsy negative are allowed.
- 3.3.4** Evidence of M1 metastatic disease.
- 3.3.5** Prior invasive malignancy except for non-melanoma skin cancer within 5 years of enrollment. Subjects must be disease-free for > 5 years.
- 3.3.6** Prior radical prostatectomy, cryosurgery for prostate cancer, or bilateral orchiectomy for any reason.
- 3.3.7** If the subject had prior androgen deprivation therapy (ADT), the subject exhibited biochemical failure while on ADT.
- 3.3.8** Prior systemic chemotherapy for the study cancer. Note that prior chemotherapy for a different cancer is allowed; however, subjects must be > 2 years post-completion of chemotherapy at time of registration. Subjects on Proscar therapy must stop to be eligible.
- 3.3.9** Major surgery planned within 3 months of registration.
- 3.3.10** Severe, active co-morbidity defined as:
 - 3.3.10.1** New York Heart Association Class II or greater congestive heart failure or active ventricular arrhythmia requiring medication.
 - 3.3.10.2** Chronic obstructive pulmonary disease (COPD) exacerbation or other respiratory illness requiring hospitalization within last 3 months or precluding study therapy at the time of registration.
 - 3.3.10.3** Acute infection. Acute infection is defined by any viral, bacterial, or fungal infection that requires specific therapy within 72 hours of initiation of the study therapy.
- 3.3.11** Previous history of liver disease including hepatitis.
- 3.3.12** Immunosuppressive therapy including systemic corticosteroids. Use of inhaled and topical corticosteroids is permitted.
- 3.3.13** Impaired immunity or susceptibility to serious viral infections.
- 3.3.14** Allergy to any product used in the protocol. If the subject has an allergy to Ciprofloxacin, another antibiotic can be substituted at the discretion of the treating physician.
- 3.3.15** Serious medical or psychiatric illness or concomitant medication, which, in the judgment of the principal investigator, might interfere with the subject's ability to respond to or tolerate the treatment or complete the trial.

4.0 REGISTRATION PROCEDURES

4.1 Registration and Enrollment

4.1.1 Subjects can be registered to the trial only after the following conditions have been met:

4.1.1.1 All inclusion/exclusion criteria of the study are met.

4.1.1.2 The Informed Consent has been signed and witnessed.

The following registration procedures will be used:

4.1.2 Once an eligible subject who meets the inclusion/exclusion criteria of the study has signed the Informed Consent, and eligibility case report form (CRF) will be completed by the clinical research staff. The Data Collection Center (DCC) in the Department of Health Services (PHS) will be notified with tentative treatment start date through the eligibility CRF.

4.1.3 The subject is considered to be enrolled into the trial if/when he receives the adenovirus injection.

4.1.4 A subject schedule will be generated by the DCC for clinical assessments/visits and medications when the subject's enrollment information is entered by the clinical staff.

4.2 Study Drug Accountability

[name] will be responsible for the preparation, allocation and disposal of the Ad5-*yCD/mufTK_{SR39}rep-hIL12* adenovirus. He will also be responsible for maintaining the study drug inventory and log. The study drug inventory will be reviewed by the DCC on a regular basis for accountability.

5.0 STUDY THERAPY AND PROTOCOL

5.1 Treatment Plan

5.1.1 Pretreatment Evaluations

5.1.1.1 History and physical examination including digital rectal exam (DRE).

5.1.1.2 Hematology- CBC/DP.

5.1.1.3 Blood chemistries- glucose, Na, K, Cl, Ca, Mg, P, CO₂, BUN, creatinine, AST/SGOT, ALT/SGPT, ALKP, bilirubin, serum protein, albumin, globulin, GFR, CPK, LDH, GGT, testosterone.

5.1.1.4 Diagnostic serum PSA.

5.1.1.5 Urinalysis, urine culture, and sensitivity.

- 5.1.1.6** Chest radiographs (PA and lateral).
- 5.1.1.7** Diagnostic imaging- bone scan and CT scan of the abdomen and pelvis within 90 days of registration.
- 5.1.1.8** Biopsy/pathology reviews- a TRUS-guided needle biopsy of the prostate (\geq 6 core) must be performed within 180 days of registration to confirm the presence of adenocarcinoma and to determine prostate volume. Biopsy cores should be kept separate, coded and submitted to Department of Pathology for analysis.
- 5.1.1.9** Molecular studies- presence of Ad5-yCD/*mutTK_{SR39}rep-hIL12* in blood by polymerase chain reaction (PCR). This is a baseline control for the post-treatment PCR assays and does not have to be completed before the subject can be enrolled.
- 5.1.1.10** Immunological studies- serum IL-12 and IFN- γ will be measured by enzyme-linked immunosorbent assay (ELISA). NK cell cytolytic activity will be measured by ^{51}Cr release or non-radioactive cytotoxicity assay. These are baseline controls for the post-treatment evaluations and do not have to be completed before the subject can be enrolled.
- 5.1.1.11** EPIC and EQ-5D instruments.
- 5.1.1.12** The subject will be required to meet with a urologic surgeon to discuss other treatments options such as salvage prostatectomy. This meeting must be documented in the patient's records.

5.1.2 Oncolytic Adenovirus-Mediated Gene Therapy

5.1.2.1 Description of Ad5-yCD/*mutTK_{SR39}rep-hIL12* Adenovirus

Ad5-yCD/*mutTK_{SR39}rep-hIL12* is a replication-competent, type 5 adenovirus (Ad5) containing a yeast CD (yCD)/mutant SR39 HSV-1 TK (HSV-1 TK_{SR39}) fusion gene in the E1 region and human IL-12 coding sequences in the E3 region (57). Expression of the yCD/HSV-1 TK_{SR39} fusion gene renders tumor cells sensitive to 5-FC and vGCV. Expression of IL-12 stimulates the innate and adaptive arms of immunity, inhibits angiogenesis, and mitigates immune suppression in the tumor milieu.

5.1.2.2 Supply of Ad5-yCD/*mutTK_{SR39}rep-hIL12* Adenovirus

Clinical-grade Ad5-yCD/*mutTK_{SR39}rep-hIL12* adenovirus was manufactured at the Baylor College of Medicine Vector Production Facility (Houston, TX) using GMP procedures. The adenovirus was supplied as a sterile, frozen liquid in vials containing 1.1 mL at a concentration of 1×10^{12} viral particles (vp) per milliliter (mL).

5.1.2.3 Storage of Ad5-yCD/mutTK_{SR39}rep-hIL12 Adenovirus

The Ad5-yCD/mutTK_{SR39}rep-hIL12 adenovirus is stored in a locked ultralow (-80°C) freezer located in a room with restricted access. An inventory log is maintained by [name].

Stability testing of the Ad5-yCD/mutTK_{SR39}rep-hIL12 adenovirus will be performed on a semi-annual basis. This will involve: 1) determination of titer, 2) genetic stability as determined by restriction digest analysis of adenoviral DNA, 3) quantification of the adenovirus cytopathic effect following infection of human prostate adenocarcinoma cells, 4) ability of the adenovirus to confer 5-FC and GCV sensitivity onto infected prostate adenocarcinoma cells, and 5) IL-12 expression following infection of human prostate adenocarcinoma cells.

5.1.2.4 Handling and Dilution of Ad5-yCD/mutTK_{SR39}rep-hIL12 Adenovirus

Human adenoviruses are Risk Group 2 (RG2) agents and should be handled using Biosafety Level 2 (BL2) procedures (67).

Thirty minutes prior to each injection, a new vial of Ad5-yCD/mutTK_{SR39}rep-hIL12 adenovirus will be removed from the storage freezer, thawed rapidly and placed on ice. The adenovirus will be diluted with sterile saline to the prescribed concentration. The diluted adenovirus will be loaded into 1 mL disposable syringes and placed on ice in a Styrofoam container. The container will be sealed with tape and transported to the treatment room.

The manufacturer, lot number and expiration date of the sterile saline used to dilute the adenovirus will be recorded.

5.1.2.5 Ad5-yCD/mutTK_{SR39}rep-hIL12 Adenovirus Dose

The treatment schema is depicted in **Figure 5**.

Dosing of the Ad5-yCD/mutTK_{SR39}rep-hIL12 adenovirus is shown in **Table 5**. The starting dose level will be 1×10^{10} vp. The interval between dosing of the first two subjects in the first cohort should be ≥ 2 weeks.

All subjects in each cohort will be evaluated for ≥ 30 days before proceeding to the next cohort. If one of three subjects experiences a dose-limiting toxicity (DLT) (defined in Section **6.3.2.3**), three additional subjects will be enrolled at that dose level. If only one of six subjects experiences a DLT at a given dose level, the dose will escalate to the next cohort of three subjects. If two subjects experience a DLT at a given dose level, the maximum tolerated dose (MTD) is exceeded. Three

additional subjects will be enrolled at the previous dose level if there were only three subjects at that dose. The adenovirus dose will be escalated to a maximum of 1×10^{12} vp.

Table 5. Ad5-yCD/mutTK_{SR39}rep-hIL12 Dosing		
Cohort	# Subjects	Adenovirus Dose (vp)
1	3 to 6	1×10^{10}
2	3 to 6	3×10^{10}
3	3 to 6	1×10^{11}
4	3 to 6	3×10^{11}
5	3 to 6	1×10^{12}

Toxicity Assessments

[figure not shown]

Figure 5. Treatment Schema. Subjects will undergo a series of pre-treatment evaluations and must meet all of the eligibility criteria to be enrolled in the study. Subjects will receive a single intraprostatic injection of the Ad5-yCD/mutTK_{SR39}rep-hIL12 adenovirus at one of five dose levels (see Table 5) on day 1. Two days later (day 3), subjects will receive a one week (7 day) course of 5-FC (150 mg/kg/day) + vGCV (1,800 mg/day) prodrug therapy. Toxicity assessments will occur twice a week during the first two weeks and then at every scheduled follow-up visit. The primary endpoint is toxicity through day 30.

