6.3.2.3 Definition of Dose-Limiting Toxicity (DLT)

Dose-limiting toxicity is defined as any of the following adverse events considered possibly/probably/definitely related to the study treatment.

6.3.2.3.1 \geq Grade 2 allergic reaction or generalized urticaria.

6.3.2.3.2 \geq Grade 2 cardiovascular or neurologic toxicity.

6.3.2.3.3 \geq Grade 3 hematologic or non-hematologic toxicity of any duration except for:

6.3.2.3.3.1 Grade 3 lymphopenia with recovery within 2 weeks.

6.3.2.3.3.2 Grade 3 anemia, leukopenia, or neutropenia that is reversible within 72 hours.

6.3.2.3.3.3 Grade 3/4 fever or flu-like symptoms that are reversible within 72 hours.

6.3.2.3.3.4 Grade 3 SGOT/SGPT that is reversible within 72 hours.

6.3.2.3.3.5 Grade 3 hyperglycemia that can be explained by patient's baseline comorbidity (i.e., diabetes).

6.3.2.3.3.6 Grade 3 hypermagnesemia that is reversible within 72 hours.

6.3.2.3.3.7 Grade 3 hypophosphatemia that is reversible within 72 hours.

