6.3.2.4 Definition of Maximum Tolerated Dose (MTD)

MTD is defined as the highest Ad5-*yCD/mutTK_{SR39}rep-hIL12* dose at which < 33% (< 1 of 3 or < 2 of 6) of any cohort develops DLT.

If 1 of 3 subjects in a cohort develops DLT, the cohort will be expanded to 6 subjects. If \geq 2 subjects out of 6 in a cohort develop DLT, MTD will have been exceeded at that dose. If there is a lower dose and if the cohort at that dose has not already been expanded to 6, the cohort will be expanded to 6 at the lower dose. If \geq 2 subjects develop DLT, MTD will have been

exceeded and the trial will stop.

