6.4.2 Study Stopping Rules

- 6.4.2.1** DLT in the first dose cohort.
- 6.4.2.2** If > 33% of enrolled subjects develop \geq grade 3 hematuria or urinary retention, the study will be stopped and the injection procedure re-evaluated.
- 6.4.2.3** Transmission of the Ad5-yCD/mutTK_{SR39}rep-hIL12 adenovirus to any subject contacts, including health care personnel.
- 6.4.2.4** Lack of availability of the Ad5-yCD/mutTK_{SR39}rep-hIL12

adenovirus.

6.4.2.5 Insufficient accrual.

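### In cohorts 2 to 5 the dosing and stopping sections count a treatment-related death as one ordinary DLT and state no hold on further injections pending review

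*Combined protocol and SAP*

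**What the plan says.** Section 6.3.2.3 defines a DLT as one of a list of adverse events "considered possibly/probably/definitely related to the study treatment". The list includes at least "Grade 3 hematologic or non-hematologic toxicity of any duration except for" a set of named exceptions. Those exceptions reach grade 3, or grade 3/4 for fever and flu-like symptoms. A fatal event is therefore a DLT, and nothing separates it from the others.

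Section 5.1.2.5 gives the dosing rule. After one DLT in three men, "three additional subjects will be enrolled at that dose level". Then: "If only one of six subjects experiences a DLT at a given dose level, the dose will escalate to the next cohort". A second DLT ends escalation: "If two subjects experience a DLT at a given dose level, the maximum tolerated dose (MTD) is exceeded". Section 6.3.2.4 repeats the expansion step and defines the MTD as the highest "dose at which < 33% (< 1 of 3 or < 2 of 6) of any cohort develops DLT".

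The DLT-based stopping rule in 6.4.2 is "DLT in the first dose cohort". The other triggers are severe hematuria or urinary retention in more than 33% of enrolled men, viral transmission to contacts, lack of product, and insufficient accrual.

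Two waiting periods are written in 5.1.2.5. One is at least two weeks between the first two men of cohort 1. The other is evaluation of every man in a cohort for at least "30 days before proceeding to the next cohort".

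Tables 9 and 10 require notice within 24 hours and a written report within 10 calendar days for any related SAE, including deaths within 30 days of injection. Section 9.0 says that a monitoring plan exists but does not set out its content.

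**The concern.** The expansion and escalation steps are written as directives. Read literally, a related death that is the only DLT in a trio leads to three more injections at the same dose. If those three men have no DLT, the dose goes up, or in cohort 5 the top dose of 1 x 10^12 vp qualifies as the MTD. The protocol is stricter at its lowest dose, where any DLT stops the study, including a grade 2 neurologic event. From cohort 2 on, at doses 3 to 100 times higher, one death stops nothing in these sections.

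The product gives the gap some weight. The safety record of 79 men in 5.1.2.8 comes from viruses without IL-12. The same section lists capillary leak and cytokine release syndromes as possibly or probably related to IL-12. Each man receives one injection, so after a death the only dosing decision left is whether to inject the next man. The written rule should answer that question.

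**Working it through.** **The plan's own figure.** Five cohorts of 3 to 6 men give 5 x 3 = 15 and 5 x 6 = 30. This matches the 15 to 30 stated in 3.1 and 8.2, and the point does not change it.

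**Does any written rule stop dosing after one related death in cohorts 2 to 5?**

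- *DLT stop (6.4.2.1):* first cohort only.
- *Hematuria or retention stop (6.4.2.2):* by cohort 2 at least 3 + 1 = 4 men are enrolled, so one event on its own is at most 1/4 = 25%, below the 33% trigger.
- *Transmission, supply, accrual (6.4.2.3 to 6.4.2.5):* not relevant.
- *Subject removal for DLT (6.4.1.4):* removes the man, not the dose level.
- *Tables 9 and 10:* reporting deadlines with no pause attached.
- *30-day evaluation (5.1.2.5):* written for the move to the next cohort. It could be read as also applying before expansion, but the text does not say so.
- *Two-week stagger (5.1.2.5):* first two men of cohort 1 only.

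None does.

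**Men who could be injected at the same dose before a review is complete, as the text stands and timing permitting.**

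| Step | 30-day evaluation applies before expansion | It does not |
|---|---|---|
| Rest of the initial trio, if the first man dies | up to 2 | up to 2 |
| Expansion men | 0 before the evaluation ends | up to 3 |
| Total | up to 2 | 2 + 3 = up to 5 |

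**Men dosed at higher levels afterwards if no further DLT occurs, at three per level.** After a death in cohort 4: 1 x 3 = 3. Cohort 3: 2 x 3 = 6. Cohort 2: 3 x 3 = 9. After a death in cohort 5 there is no higher dose, but 1 of 6 satisfies the MTD definition. Escalation comes at least 30 days after the expansion men are dosed, so the written report on a promptly discovered death would already be due.

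**How often might this arise? Illustration only.** The documents give no death or DLT rate for this virus. Let d be the assumed related-death risk per man, o the risk of any other DLT, and t = d + o, the same at every dose. Cohort 1 must be free of DLTs, and de-escalation cohorts are ignored.

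- A level passes without a death: a = (1-t)^3 + 3o(1-t)^5.
- A death is the only DLT in a level's first three men: e = 3d(1-t)^2.
- The level then passes with the death in it: b = 3d(1-t)^5.
- Chance that the situation arises in cohorts 2 to 5: (1-t)^3 x e x (1 + a + a^2 + a^3). For a level passing with a death, put b in place of e.

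Worked case, d = 0.01 and o = 0.10: (0.89)^3 = 0.7050, a = 0.8725, e = 0.02376, and the sum in a is 3.298. The product is 0.7050 x 0.02376 x 3.298 = 0.055.

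| Assumed d | Arises, at o = 0 / 10% / 20% | Level passes with a death, same o |
|---|---|---|
| 0.1% | 1.2% / 0.6% / 0.2% | 1.2% / 0.4% / 0.1% |
| 1% | 10.9% / 5.5% / 2.3% | 10.6% / 3.9% / 1.1% |
| 2% | 19.9% / 9.9% / 4.1% | 18.7% / 6.8% / 1.9% |

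The spread, from 0.1% to 19.9%, reflects the assumptions and is not an estimate for this trial.

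**The case against.** Several points on the other side stand.

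- **The hold may exist elsewhere.** A reader might infer that the trial has no provision for pausing after a death. The documents do not support that. The Section 9.0 plan is not reproduced and could contain one, and the IRB or FDA could impose one. What the text shows is that the three sections governing dosing neither state a hold nor cite the plan.
- **Deaths are not singled out in reporting.** One might argue that the protocol treats a related death as special for reporting but ordinary for dosing. Table 9 gives every related SAE the same deadlines, so that contrast fails.
- **Rapid dosing is unlikely.** The IRB is told within 24 hours of discovery, well before the 10-day report. Trial 1 enrolled 16 men at this site over about two years, roughly 0.22 per 10 days. If accrual were Poisson at that rate, three or more men in 10 days would have a chance of about 0.15%, rising to 1% at double and 3% at triple the pace. Trial 1's average includes any waits between cohorts, so this too is only illustrative.
- **A death is not expected.** Trial 1 had no DLTs or SAEs in 16 men at up to 1 x 10^12 vp, without IL-12. The two IL-12 deaths cited in Section 1.3 followed systemic protein, and the protocol says that local IL-12 was well tolerated. Nothing here shows that the treatment is likely to be fatal.
- **Equal weight for all DLTs comes with the design.** Section 8.2 calls cohorts of 3 to 6 standard. That explains the rule, but a death override can be added without changing the design.

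These points lower the urgency. They do not supply the missing instruction.

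**Conclusion.** The point holds for the supplied protocol text. In cohorts 2 to 5, Sections 5.1.2.5, 6.3.2.4 and 6.4.2 give a related death the weight of any single DLT and state no hold pending review. As written, they allow up to 2 further same-dose injections if the first man of a trio dies, or up to 5 if the 30-day evaluation does not cover expansion. With no further DLT, 3 to 9 men would follow at higher doses after a death in cohorts 2 to 4.

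The counts follow from the text and are upper limits that depend on timing. The probabilities rest on assumed rates, and the finding does not depend on them. This is an inexpensive safety improvement to consider. It does not show that the design is unsound or that men would in practice be injected before review.

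**What to change.** Add to 6.4.2, with cross-references in 5.1.2.5 and 6.3.2.4: any death possibly, probably or definitely related to study treatment, at any dose level, immediately suspends all further injections, including the remaining men of the current trio and any expansion men. The suspension lasts until the death has been reviewed with the IRB and FDA and a decision to resume, de-escalate or stop is recorded. Expansion or escalation applies only after that decision. Extending the hold to related life-threatening SAEs is optional.

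If the Section 9.0 plan already contains such a hold, cite it in these sections instead.

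The cost is one sentence and two cross-references, or a citation. No tests or patients are added, and the 15 to 30 range is unchanged. The downside is a possible pause in accrual if a related death occurs.
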